4.0 STUDY PROCEDURES

Please refer to Appendix B for Time and Event Schedule detailing when study tasks will be performed.

4.1 Screening/Baseline Visit procedures

- Informed consent and assent for study participation will be obtained from the parent/guardian and child respectively
- We will perform a clinical interview and then confirm diagnosis with MINI-KID.
- The following scales will be administered:

Diagnostic:

- A SCID-5 (Structured Clinical Interview for DSM-5) interview will establish diagnosis of major depression and rule out exclusionary psychiatric disorders.

Efficacy scales to establish a baseline:

- Children's Depression Rating Scale Revised (CDRS-R), a commonly used, highly regarded and validated measure of depression as one of our primary outcome measures.
- Hamilton Depression Rating Scale (HAM-D), one of the most widely used depression rating scales in clinical care and research. This will help measure the primary outcome.

Cognitive / Safety:

- Cognitive assessments will include MMSE, Trails B and List Generation.
- Safety Assessments will include the C-SSRS, semi-structured interview for NSSIB, and a medical review of symptoms including items commonly seen in the literature. [24]
- Medical review for metallic implants, general medical history, and medication review.
- Physical exam including vital signs (temperature, respiratory rate, oxygen saturation, blood pressure, heart rate, weight).
- Neurological exam performed by a trained psychiatrist and has experience providing iTBS. It entails the neurological history for epilepsy, seizures, including febrile seizures in infancy and self-limited isolated seizures in childhood, reason, time course and dose of treatment with anti-epileptic medications, other significant neurological illness that have cause that is infectious (meningitis), metabolic (electrolyte abnormalities), genetic/inherited (syndromes like Downs or 22q deletion syndromes) that are associated with mental illness, dementia and psychosis, any significant delay in cognitive, motor or sensory development. The neurological exam looks at Cranial nerves: I, II, III, IV, V, VI, VII, VIII, IX, X, has a motor exam (strength and symmetry, upper and lower extremity muscle groups), sensory exam (fine touch, pain, temperature, and proprioception), and reflex exam. Cognitive function is also evaluated—Mini Mental Status of Folstein to include alertness, orientation, short/long-term memory, attention, concentration, fund of knowledge.
- Urine pregnancy test for females of childbearing potential
- Urine Drug Screen
- Study team will ask subjects to speak with their regular doctors and have caregivers sign release of information forms if they agree.
- Patients who sign consent for a screening will receive a unique subject ID code. It will be coded as “ERAxx” where “xx” represents the number of sequential enrollment “01, 02, etc.” There will be a key that links subject’s identifying information (name, date of birth) and subject ID stored securely with other study materials, that only those with permission have access to on a need-to-know basis.

4.2 Intervention/Treatment procedures (by visits)

- On the first treatment day: Prior to initiation of iTBS administration, the physician will establish 100% of motor threshold. iTBS will then be administered starting at 100% of motor threshold, increasing to 120% of motor threshold while adjusting the coil position to minimize side effects.
- The remaining 19 iTBS treatments: These will be delivered over a four week period, with five treatments delivered weekly by a UNC rTMS-trained physician Monday through Friday.
- General information about the entire treatment phase of study that is not visit specific: Each treatment will follow the iTBS protocols established by MagVenture, Inc. and treatment will be provided at 120% of motor threshold at all 20 treatment visits.
- Patients will undergo CDRS-R, HAM-D, and cognitive assessments once weekly during the treatment phase, starting on their fifth treatment day, and each week from that time point depending on which day of the week they start treatment.
- Patients will be assessed prior to every treatment for side effects or safety-related symptoms, as well as review of concomitant medication.

- Vitals will be taken prior to every treatment administration during all 20 treatment days. Weight will be obtained once per week during the treatment phase. Per investigator discretion, weight may be obtained at additional timepoints during the treatment phase or unscheduled visits to ensure safety of the subject.
- UDS and urine pregnancy tests can be done at any time due to investigator discretion for safety purposes. Pregnancy risk assessment will be documented at every visit for females of childbearing potential.

4.3 Follow- up procedures (by visits)

- At a 1-week post treatment follow-up visit, the CDRS-R, HAM-D, cognitive and safety assessments will be completed (MMSE, List Generation, Trails B, C-SSRS, NSSIB interview). In addition, vitals including weight will be taken, a physical exam performed, and AE and concomitant therapy review will be done.
- At a 4-week post treatment follow-up visit, the CDRS-R, HAM-D, cognitive and safety assessments will be completed (MMSE, List Generation, Trails B, C-SSRS, NSSIB interview). In addition, vitals including weight will be taken, a physical exam performed, and AE and concomitant therapy review will be done.
- At a 12-week post treatment follow-up visit, the CDRS-R, HAM-D, cognitive and safety assessments will be completed (MMSE, List Generation, Trails B, C-SSRS, NSSIB interview). In addition, vitals including weight will be taken, a physical exam performed, and AE and concomitant therapy review will be done. A Patient/Caregiver satisfaction questionnaire will be done to help improve future study designs.

4.4 Unscheduled visits

Any of the assessments used above may be used for an unscheduled visit, depending on the reasons for visit and safety needs. If the participant at any time is experiencing an AE or another reason for safety concern, in which the investigator deems is probably related to the study treatment, an unscheduled visit can be scheduled for a safety review. Appropriate referrals can also be made for ongoing care should a safety concern arise that is not study related.

4.5 Concomitant Medication documentation

Concomitant psychotropic medications will be documented starting 1 month prior to screening and enrollment. In addition, this will be monitored and recorded during every visit in which participant is enrolled in the study. Non-psychotropic medications for other significant medical conditions or birth control will also be monitored. There are a wide variety of medications that can decrease the seizure threshold such as antihistamines, anticholinergics, and cephalosporins among others – there is no absolute contra-indication for TMS when taking these medications in adults. However, the decision to continue treatments will be done at every visit at the PI's discretion of clinical need and risk potential. Monitoring will be done for benzodiazepines, antidepressants, stimulants, and antipsychotics, which would preclude either initiation or continuation of the study. Please see Appendix A for more detailed information.

4.6 Rescue medication administration: N/A

4.7 Subject Completion / Withdrawal procedures

Subjects who complete the study will be reminded of the study team's contact information should they have any questions in the future. Files will be kept under lock and key in a locked office in a secure facility for the

required amount of time according to GCP (Good Clinical Practice) principles and FDA regulations. For those wishing to withdraw from the study early, a termination visit will be scheduled to ensure safety, proper follow up, review adverse effects, and medications. CDRS-R, HAM-D, all cognitive, and safety assessments will be performed for final data capture if the patient agrees.

Patients will be withdrawn by investigators if they miss 20% of planned treatments, for noncompliance, or any other issues the PI determines can cause harm to the patient.

We will not replace discontinued participants. We will use the data we have up until discontinuation.

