3.2 Allocation to Treatment Groups and Blinding (if applicable): N/A

3.3 Study Duration, Enrollment and Number of Subjects

5 subjects are expected to enroll. The total study participation will be over the course of 16-17 weeks, including the 24 study visits. The iTBS treatment itself will last a few minutes, and additional time will be allocated for machine set-up and additional review of symptoms as needed. Once per week during the treatment phase, subjects will also have additional cognitive and safety assessments done for safety monitoring that will last approximately 1 hour.

Given that subjects will need to come in 4 consecutive weeks Monday-Friday for treatments, it is likely one patient will be treated at a time. With the need to enroll and complete all data collection within a year, minus startup time, it is feasible to enroll 5 patients. In addition, iTBS has not been used in patients younger than 16 before, and while there is no safety concern for this, it would make sense from a safety perspective to start with a smaller number of participants. The data used from this study will then be used to pursue larger grant opportunities such as R01 to enroll more subjects that will allow for statistical significance calculations.

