5.3 Pharmacokinetic Evaluation: N/A

6.0 STATISTICAL CONSIDERATIONS

6.1 Primary Endpoint

Differences in CDRS-R and HAM-D scores will be divided by the standard deviation for effect size (which will not be scaled for statistical significance given the sample size). Descriptive statistics and repeated ANOVA will be used to evaluate efficacy. Tolerability will be evaluated examining safety and adverse events at every study visit. Given the novelty and duration of treatment, it is more likely 5 patients will be able to participate and provide enough data for future research that is funded to expand sample size.

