6.3 Statistical Methods

- **Baseline Data:** CDRS-R, HAM-D, and other cognitive and safety assessments will be used at screening to capture baseline data.
- **Efficacy Analysis:** As this is an uncontrolled study design, the investigators understand that any change in scores or observed improvement in symptoms may not be necessarily attributable to the treatment received. Thus, efficacy analysis will be described in this context. The investigators feel that a larger study would be indicated which may be sham controlled. Repeated measures ANOVA will be used to compare depression rating scores from each of the treatment weeks compared to baseline, as well as comparing scores between follow up visits and baseline and end of treatment weeks. Pearson's r coefficient will be used to determine correlation between, CSSR-S scores, and primary endpoints (CDRS-R & HAM-D). Descriptive statistics to identify if NSSIB is present since the subject's last visit at baseline, during the interventional period and follow ups, will be used. It is worth noting that use of ANOVA analysis has been recommended by a biostatistician, but due to a small sample size, longitudinal data will not have adequate statistical power. In addition, confidence intervals will be large and results will be uninformative regarding statistical power. This uncertainty may contribute to a future study sample size that is still too small for statistical power, but a larger sample size than this protocol.
- **Pharmacokinetic Analysis:** N/A
- **Safety Analysis:** Measurement of safety is a continuous process starting with screening. Medical review of symptoms occurs at every visit. In addition, should safety concerns related to study treatment occur, additional unscheduled safety visits can be performed. Additional assessments are done weekly during the 4-week treatment phase.
- **Personnel:** Study coordinator will complete data entry into RedCap system and oversee data management. The Principle Investigator will do oversight. A TraCS biostatistician ([name]) will complete data analysis and computations and will work with the study team throughout the duration of study activities and completion.

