- Missing Data and Protocol Violations: Data will be collected in multiple formats – on paper and later electronically. Paper data will include various scales and assessments. There will be two members of the investigation team during assessments and scale administration, which can assist with looking over the data. Paper documents will be labeled without any personal health information or other sensitive identifying information outside of the study team. These documents will be stored in a locked cabinet in a locked office. If there is any missing data, we will refer to the stored paper documents. If data continues to be missing, we are planning to mitigate selection bias by remarking clearly in our results and discussion that consideration must be given to this fact. Any protocol violations will be assessed by the Principal Investigator, will be submitted to the IRB, and a discussion will be had on how to proceed with the study.
- Other: For any missing data, rationale and documentation will be provided in the database (RedCap) and source documentation.

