6.4 Sample Size and Rationale

This is a pilot study to measure the efficacy, duration, safety and feasibility iTBS in 5 adolescents with MDD. It will not be powered to show significance. The study may provide important preliminary data for NIH (National Institute of Health) R01 applications. In addition, safety and tolerability will be documented for all 5 subjects to support the expansion of recruitment for future research. The sample size was determined by several factors. This is a novel study treatment for adolescents, thus using smaller sample size will help evaluate safety and feasibility in a safe manner. In addition, realistic logistical factors were considered: there is time commitment of treatment required, our patient pool at our clinic, and realistic ability to enroll and complete the study in a year's given time. We expect to have 5-10 patients consented, accounting for potential screen failures. We also have parents calling our clinic asking for TMS/ iTBS treatment but insurance will not cover it, so we are confident we will be able to successfully recruit. All statistical estimates of population parameters will be tabulated along with corresponding confidence intervals.

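### Section 4.7 keeps a withdrawn subject's ratings, but repeated measures ANOVA as conventionally fitted drops that subject, and 6.1–6.3 name no fit that would retain the data

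*Combined protocol and SAP*

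**What the plan says.** Section 4.7 sets the rule for subjects who leave: "We will not replace discontinued participants" and "We will use the data we have up until discontinuation". It also schedules a termination visit, at which "CDRS-R, HAM-D, all cognitive, and safety assessments will be performed for final data capture if the patient agrees".

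The analysis is in Section 6. For the primary endpoint, 6.1 gives an effect size (score difference over its standard deviation) and adds: "Descriptive statistics and repeated ANOVA will be used to evaluate efficacy". Section 6.2 pairs descriptive statistics with repeated measures ANOVA for suicidality and durability, and uses descriptive statistics alone for NSSIB. In 6.3, "Repeated measures ANOVA will be used to compare depression rating scores from each of the treatment weeks compared to baseline"; the same sentence goes on to compare follow-up visits with baseline and with the end of treatment.

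On missing data, 6.3 first has staff return to the paper records. If values are still missing, "we are planning to mitigate selection bias by remarking clearly in our results and discussion" that readers must bear this in mind. Nothing in Section 6 says how a subject with incomplete ratings enters the ANOVA.

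Three further facts bear on the point. In Section 3.3, "5 subjects are expected to enroll". Section 5.1 and Appendix B schedule eight ratings per subject: screening, four weekly, three follow-up. Section 8.0 lets investigators remove a subject who gets worse or does not benefit, and the feasibility criterion in Section 2.0 tolerates one withdrawal in five.

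**The concern.** The withdrawal rule and the analysis method were not written to fit each other. The conventional within-subject ANOVA works on a complete subject-by-visit table. A subject who leaves after week 2 has three ratings that 4.7 says will be used, yet in a conventional ANOVA over all eight ratings that subject contributes none. A single missed rating without withdrawal has the same effect.

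The loss need not be random. If a subject is removed for doing badly, a completers-only ANOVA describes the others, even at weeks 1 and 2 when the removed subject was rated. A remark in the discussion discloses this but does not correct it. Sections 3.3 and 6.4 intend these estimates to support larger grant applications, and each subject is 20% of the sample.

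**Working it through.** The plan gives no power, effect size or dropout rate, so there is no stated figure to reproduce. The check is of the method.

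**1. What the conventional fit loses.** Inputs: n = 5 (3.3) and k = 8 ratings (5.1, Appendix B). Degrees of freedom are k − 1 and (n − 1)(k − 1).

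- Complete data: 5 × 8 = 40 ratings; df 7 and 4 × 7 = 28.
- One subject dropped: 4 × 8 = 32 ratings; df 7 and 3 × 7 = 21.
- Two dropped: 3 × 8 = 24 ratings; df 7 and 2 × 7 = 14.

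A standard repeated measures ANOVA routine (statsmodels), given simulated 5 × 8 data with one subject cut off after week 4, refuses to run because the data are unbalanced.

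**2. What other fits keep.** For the same data, 32 + 5 = 37 ratings were taken. A least-squares ANOVA with subject and visit factors uses all 37 (residual df 37 − 5 − 7 = 25). A random-intercept mixed model also uses 37 ratings and 5 subjects. A conventional ANOVA restricted to baseline and the four treatment weeks keeps all five subjects (df 4 and 16), but only because the withdrawal came after week 4.

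**3. How often it would arise.** The dropout rate is an assumption. The chance of at least one withdrawal in five is 1 − (1 − d)^5: 23%, 41%, 67% and 83% for d = 5%, 10%, 20% and 30%. For isolated missed ratings, if each of the seven post-baseline ratings is missed independently with probability 5% (assumption), a subject is complete with probability 0.95^7 = 0.698, so about 5 × 0.698 = 3.5 subjects remain. At 2% the figure is 4.3, and at 10% it is 2.4.

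**4. Precision.** For a stand-alone paired interval, t/√n goes from 2.776/√5 = 1.242 to 3.182/√4 = 1.591, which is 28% wider. With the ANOVA's pooled error it goes from 2.048/√5 = 0.916 to 2.080/√4 = 1.040, about 14% wider. The second figure belongs to the method the plan names.

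**5. Direction of bias (illustrative).** Assume a mean fall of 5 points per week, slopes varying between subjects with SD 3, rating error SD 4, and the subject with the least observed improvement leaving after week 2.

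- The SD of week-2 change is √((2 × 3)² + 2 × 4²) = √68 = 8.25.
- The expected maximum of five standard normal values is 1.163, so removing the worst subject shifts the mean of the other four by 1.163 × 8.25 / 4 = 2.4. Week-2 change is −12.4 in those retained and −10.0 in all five rated. Simulation agrees.
- If the SD of 3 is on starting level instead of slope, the shift is 1.163 × √32 / 4 = 1.6, giving −11.6.
- If the leaver has the lowest true slope, it is 1.163 × 6 / 4 = 1.7, giving −11.7.

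**6. What a mixed model recovers (slope case of step 5).** At week 2 all five subjects are observed, so a model with a separate mean for each visit returns the all-rated −10.0. At week 4 the true change is −20.0; simulation gives −23.0 for completers and −21.9 for the random-intercept model (assumed variance ratio 1.5). The remaining bias is 1.9 of 3.0, about two thirds.

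**The case against.** A reader might infer that 4.7 and 6.3 cannot both be followed. The documents do not go that far. They nowhere specify complete cases, listwise deletion or one eight-level model, and 6.3 describes sets of comparisons that could be run over shorter windows. The refusal in step 1 is a property of one routine that the plan never names, and step 2 shows fits that keep every rating. The defect is an unstated fitting rule that conflicts with 4.7 under the conventional reading.

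A reader might also infer that the withdrawn subject is lost altogether, or that the termination-visit rating is barred from analysis. Neither is supported. The descriptive statistics, the effect size, and the safety and feasibility summaries can all use the subject's data. Section 4.7 collects the termination rating precisely so that it is captured. What is missing is a rule placing it on the visit grid of Appendix B.

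The direction of bias is conditional. Section 8.0 permits removal for poor outcome but does not require it, and sessions missed or noncompliance can also end participation. The simulation assumes that the worst subject leaves, so its size is not a forecast. With no withdrawal and no missed rating, the issue never arises.

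Finally, the consequence is limited: on sample size, 6.4 says "It will not be powered to show significance", 6.3 already concedes wide intervals and no attribution to treatment, and the feasibility criterion does not use the ANOVA.

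All of this stands, and it limits the point without removing it. Several fits are possible, they can give different answers with five subjects, and the plan does not choose.

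**Conclusion.** The concern holds in limited form. The plan promises to use partial data but names an inferential method whose conventional fit omits any subject with a gap, and it gives no rule that carries out the promise within that method. Under that fit one withdrawal costs 20% of the sample, including ratings already taken (five, if the subject leaves after week 4), and widens the ANOVA-based interval by about 14%.

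A tilt towards benefit at the early weeks is possible if removal follows poor outcome. The figure of about 2.4 points at week 2 rests wholly on the assumed slope, variances and departure rule; the variants in step 5 give about 1.6 to 1.7. The documents supply no dropout rate, so how likely this is cannot be fixed. For an unpowered pilot this is a change worth making before the data are seen, not a critical fault.

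**What to change.** In 6.1–6.3, replace repeated measures ANOVA with a linear mixed model fitted to every rating obtained: visit as a categorical fixed effect, a random intercept for subject, and small-sample degrees of freedom. State that the termination-visit rating is assigned to the nearest scheduled week, and which value is used if that week already has one. Show the number rated beside each visit mean, with individual trajectories for all five subjects.

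The cost is a few sentences and a different procedure for the biostatistician already engaged; no further data are needed.

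The plan should state the downside. The model assumes that ratings are missing at random and that a simple covariance is adequate; five subjects will hardly support a richer one. It restores the visits at which the withdrawn subject was rated. At visits after withdrawal only the remaining subjects are observed under any method, and if subjects improve at different rates the model corrects the bias only in part (step 6). The remark about missingness in the results and discussion should therefore stay.

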- Serious side effects (seizures): 0% in kids treated with iTBS in studies performed so far. The risk for seizure increases if someone has central nervous system disorders or a history of epilepsy. In regular Transcranial Magnetic Stimulation (TMS), the risk is .06%

There is no known risk for increasing suicidality by using iTBS. In addition, patients who are imminently suicidal will not be allowed to participate in the study. Appropriate referrals will be made should this happen.

Potential Benefits:

Potential benefits include a reduction in depressive symptoms. This in turn can alleviate other impairments in functioning that are caused by depression; such as better sleep, appetite, socialization, school and work functioning, and overall wellness. This will be measured and tracked through HAM-D and CDRS-R assessments (more information on these assessments in section 5.2)

Additional Follow-up: Patients will continue to be seen by their regular provider and specialist, and may find benefit in working with an additional treatment team for closer follow-up.

Risk /Benefit Assessment

Due to the need to expand treatment for MDD and similarities between the risks and benefits to other treatment options currently available or other clinical studies, it has been determined that the potential benefits outweigh the potential risks.

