2.0 STUDY OBJECTIVE

The purpose of the study is to determine the efficacy/durability, the safety, and the feasibility of iTBS in 5 adolescents with MDD.

Specific Aims.

Aim 1. Investigate the efficacy and durability of effects by estimating the magnitudes of pre-regimen vs. post-regimen longitudinal changes in CDRS-R, HAM-D, and NSSIB evaluations.

Hypothesis 1: Adolescents with MDD will show improvement in symptoms over 20 iTBS sessions as measured by the Children's Depression Rating Scale Revised (CDRS-R), HAM-D and NSSIB measures.

Hypothesis 2: Adolescents with MDD will show reduction of depressive symptoms will persists through the 12 week follow up period of the study.

Hypothesis 3: Adolescents with MDD who demonstrate NSSIB at the start of the trial will show reduction in NSSIB after iTBS treatments.

Aim 2. Investigate safety of the treatment regimen by assessing suicidality with the Columbia Suicide Severity Rating Scale (C-SSRS).

Hypothesis 1: Adolescents with MDD will show reduction in suicidal thoughts and behavior with iTBS treatment as measured by the Columbia Suicide Severity Rating Scale (C-SSRS) and a psychiatrist's clinical assessment.

Aim 3. Investigate treatment feasibility by assessing treatment completion and withdrawal.

Hypothesis 1: iTBS will be considered feasible if: a.) 15/20 (75%) iTBS treatment sessions are completed by all subjects, and; b.) no more than one of five subjects (20%) withdraw from iTBS due to intolerable side effects or persistent symptoms of MDD.

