6.2 Secondary Endpoint

- To evaluate the reduction of suicidality in adolescents with MDD: This will be done with descriptive and repeated measures ANOVA.
- To assess durability of antidepressant effect: This will be done with descriptive and repeated measures ANOVA.
- To evaluate the change in Non-suicidal Self Injurious Behavior (NSSIB): This will be evaluated with descriptive statistics.
- Evaluation of adverse events will be performed at every visit and documented according to GCP guidelines. Appropriate follow up and referrals will be made as needed.

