8.0 STUDY INTERVENTION ADMINISTRATION

Treatment compliance and Adherence: A medication review will be performed prior to each treatment administration for treatment compliance. If 20% of planned sessions are missed, contraindicated medications are used, or there is worsening or lack of benefit, investigators can remove subject from the study. A trained study clinician will do administration of treatment.

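### A subject who leaves because suicidality worsens can be missing from the Aim 2 C-SSRS result: the exit rating is conditional, is not stated for investigator withdrawals, and has no place in the analysis

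*Combined protocol and SAP*

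**What the plan says.** Aim 2 in section 2.0 is the safety aim. Its hypothesis is that suicidal thoughts and behaviour fall, "as measured by the Columbia Suicide Severity Rating Scale (C-SSRS) and a psychiatrist's clinical assessment". Section 6.2 gives the analysis: "To evaluate the reduction of suicidality in adolescents with MDD: This will be done with descriptive and repeated measures ANOVA". Appendix B schedules the C-SSRS at screening, at the end of each of the four treatment weeks and at the three follow-up visits. It has no column for a termination visit.

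Section 4.7 does not replace subjects who discontinue and says "We will use the data we have up until discontinuation". It arranges a termination visit for subjects who choose to leave early and repeats the safety scales there if the patient consents to it. Section 4.1 lists the C-SSRS as a safety assessment, so an exit C-SSRS is planned on that route. A separate paragraph of 4.7 has investigators withdraw subjects for, among other reasons, anything the PI judges harmful. Section 8.0 adds that if sessions are missed, contraindicated medication is used, "or there is worsening or lack of benefit, investigators can remove subject from the study". Neither text mentions an exit assessment.

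Sections 3.1 and 4.4 allow any scale at an unscheduled visit. For missing data, section 6.3 relies on checking the paper records, documenting the reason and a caution in the report. On size, section 3.3 says "5 subjects are expected to enroll" and section 6.4 says "It will not be powered to show significance".

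**The concern.** In a safety aim built on suicidality, worsening is the outcome that most needs to be seen, and it is also a reason why a subject may leave. If leaving also ends the ratings, the summary rests on those who stayed and on the leaver's earlier, better scores. The event would still be in the adverse event record, but nothing in section 6.2 ties that record to the suicidality result.

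The data are meant to justify a larger adolescent study. In a group of five, a report that nobody worsened reads very differently from a report that one subject did.

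**Working it through.** **Inputs.** Five subjects (3.3, 6.4). C-SSRS occasions from Appendix B: 1 + 4 + 3 = 8. The plan gives no expected C-SSRS change, no SD and no rate of exit for suicidality, so it has no figure of its own on this point to reproduce. Its related arithmetic is consistent: visits 1 + 20 + 3 = 24, as stated in 3.3, and 1/5 = 20%, as stated in Aim 3.

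**Step 1. Is an exit C-SSRS stated, and is it used?**

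| Route | Exit C-SSRS stated? | Place in the Aim 2 analysis? |
|---|---|---|
| Subject chooses to leave (4.7) | Yes, if the subject agrees | None given |
| Investigator withdraws for harm (4.7) | No | None given |
| Investigator removes for worsening (8.0) | No | None given |
| Unscheduled visit (3.1, 4.4) | Optional | None given |

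Section 3.1 offers unscheduled visits for any safety concern. Section 4.4 ties them to events thought probably related to treatment and mentions referral for unrelated concerns. On the 4.4 wording, a crisis attributed to the underlying depression need not produce a rating.

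**Step 2. How old can the last scheduled rating be?** About 7 days during treatment. In follow-up, from week 1 to week 4, (4 - 1) x 7 = 21 days; from week 4 to week 12, (12 - 4) x 7 = 56 days, before the 3-day visit windows.

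**Step 3. Effect on a count of subjects who worsened.** The plan defines no such count; it is used here to show size. Exact (Clopper-Pearson) 95% intervals; for 0/n the upper limit is 1 - 0.025^(1/n).

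- Leaver kept on an earlier, unworsened rating: 0/5, upper limit 1 - 0.025^(1/5) = 52%.
- Leaver dropped, as a complete-case ANOVA would do: 0/4, upper limit 1 - 0.025^(1/4) = 60%.
- Exit counted as worsening: 1/5 = 20%, interval 0.5% to 72%.
- Two such exits counted: 2/5 = 40%, interval 5% to 85%.

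**Step 4. Effect on mean change.** Assume that four subjects each improve by 1 point and the fifth leaves after worsening by w points.

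- Fifth dropped: -4/4 = -1.0.
- Fifth's earlier rating used, with change 0 or -1: (-4 + 0)/5 = -0.8, or (-4 - 1)/5 = -1.0.
- Exit rating included, (-4 + w)/5: -0.6, -0.4, -0.2, 0.0 and +0.2 for w = 1, 2, 3, 4 and 5.

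The sign reverses only when w exceeds four times the improvement of each of the others.

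**Step 5. How likely is at least one worsening subject?** 1 - (1 - p)^5 for an assumed per-subject risk p: 23% at p = 5%, 41% at 10%, 67% at 20%. This is the chance that someone worsens, not that the worsening goes unrecorded, so it is an upper bound on the problem at each p.

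**The case against.** The strongest reply is that the plan already has several ways to see the event. Section 4.7 plans final ratings that include the C-SSRS, and using data up to discontinuation does not clearly exclude them. Weekly ratings may catch a rise before the subject goes; depression worsening seen on the weekly CDRS-R or HAM-D would be found at the visit where the C-SSRS is also due. The Aim 2 hypothesis adds a psychiatrist's assessment, psychiatrists review symptoms at every visit, and adverse events are listed under the same 6.2 heading. Section 8.0 is permissive and does not name suicidality. No section says that a subject hospitalised in follow-up is withdrawn, so that subject might still attend the next visit. The intervals in Step 3 overlap almost entirely, and section 6.3 already concedes that intervals will be wide.

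Much of this stands. It rules out the stronger reading that a reader might infer, that a leaver is always scored only on ratings made before the crisis. A reader might also take "patients who are imminently suicidal will not be allowed to participate in the study" as an exit rule; it reads more naturally as a restatement of the entry exclusion in 3.4, so the point rests on 4.7 and 8.0.

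What the reply does not do is close the gap. The exit rating is conditional on one route and unstated on the others, the psychiatrist's assessment has no analysis, and no text links an adverse event or a withdrawal reason to the suicidality result. Wide intervals do not excuse an observed count that leaves out a known event.

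**Conclusion.** The point holds in conditional form. If a subject leaves because suicidality worsens, and an exit C-SSRS is either not obtained or not used, the Aim 2 C-SSRS summary can show a reduction while omitting that worsening. One such subject is 20% of the sample. On the assumed values in Step 4, the mean change would be -0.8 to -1.0 instead of -0.6 to +0.2.

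Two further inferences are not supported. The plan contains no carry-forward rule and no worsened/not-worsened classification, so it cannot be said to score a leaver as unchanged or improved; it leaves the handling open. Nor does the omission always favour iTBS: if the rise is rated before departure and that rating is kept, the data include it, and early exit may also leave out a later recovery. The favourable direction applies when the worsening itself goes unrated or unused.

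The size rests on assumed changes and on one or two exits of this kind. No sample-size figure is affected. It is a worthwhile, inexpensive clarification of the analysis.

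**What to change.** Add to section 6.2, with a matching sentence in 4.7:

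- **Use every rating.** Any C-SSRS from a termination or unscheduled visit enters the Aim 2 descriptive analysis, for example through each subject's worst post-baseline rating, whether or not it fits a scheduled ANOVA time point.
- **Report a count over all enrolled subjects.** Beside the mean change, give the number with worsened suicidality. Subjects with an exit C-SSRS are classified from their ratings against baseline, by a definition fixed before analysis. A subject without one is counted as worsened if withdrawal, removal or psychiatric hospitalisation was recorded as due to worsening suicidal ideation or behaviour. Any subject with a recorded suicide attempt or death by suicide after baseline is counted as worsened.

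Limiting the withdrawal rule to subjects without an exit rating avoids reclassifying someone whose rating shows no change.

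The cost is a few sentences. The adverse event log is already kept, and the Aim 3 criterion already needs withdrawal reasons. Who is withdrawn and how they are treated stay as they are. The suicidality result may look less favourable, partly because a worst rating is the extreme of up to 4 + 3 = 7 scheduled post-baseline ratings plus any extra ones; it should therefore stand beside the mean change and not replace it. The count also cannot capture an event that nobody recorded after the subject left, and the report should say so.
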